### 7.1. Adverse Events Analyses

Adverse events analyses including the analysis of adverse events (AEs), serious AEs (SAEs) and other significant AEs will be based on GSK Core Data Standards. The details of the planned displays are provided in [Appendix 10](#): List of Data Displays.

AEs will be graded according to the CTCAE, Version 4.0. Adverse events will be coded to the PT level using the MedDRA dictionary. The relationship of AE system organ, preferred term, and verbatim text will be listed. The subject numbers for individual AEs will be listed.

A summary of number and percentage of subjects with any adverse events by maximum grade will be produced. AEs will be sorted by System Organ Class (SOC) and Preferred term (PT) in descending order of total incidence.

The relationship between MedDRA SOC, PT, and Verbatim Text will be listed.

A listing of All AEs will be provided.

Serious adverse events by system organ class and preferred term (number of participants and occurrences) will be summarized. All serious adverse events (SAEs) will be tabulated based on the number and percentage of subjects who experienced the event. The summary tables will be displayed in descending order of total incidence.

Separate listings will be generated for all fatal SAEs and non-fatal SAEs.

### 7.2. Adverse Events of Special Interest

A comprehensive list of MedDRA terms based on clinical review will be used to identify each of the AESI.

The events of special interest include:

- Encephalopathy
- Thrombocytopenia
- Hemorrhages
- Diarrhea

- Nausea & Vomiting
- Constipation
- Infections
- Neutropenia
- Fatigue
- Anemia

One summary giving number and percentage of subjects for each of these AESI will be provided. Separate listing for each of the AESI will also be provided.

### 7.3. Clinical Laboratory Analyses

Laboratory evaluations will be based on GSK Core Data Standards. The details of the planned displays are in [Appendix 10](#): List of Data Displays.

The assessment of laboratory toxicities will examine the following laboratory tests as specified in [Table 2](#) below.

**Table 2 Laboratory Tests**

Hematology
Platelet count
White blood cell (WBC) Count (absolute)
Hemoglobin
Automated WBC Differential:
Neutrophils
Lymphocytes
Monocytes
Eosinophils
Basophils
Red blood cell (RBC) Indices (at screening and if Hemoglobin decrease $\geq 2$ g/dL compared to baseline):
Mean corpuscular volume (MCV)
Mean corpuscular hemoglobin (MCH)
Mean corpuscular hemoglobin concentration (MCHC)
Reticulocytes
RBC

Clinical Chemistry			
Blood urea nitrogen	Potassium	Aspartate aminotransferase (AST)	Total and Direct bilirubin 
Creatinine	Chloride	Alanine aminotransferase (ALT)	
Glucose, random	Total CO2	Albumin	
Sodium	Calcium 	Alkaline phosphatase (ALP)	
Magnesium	Phosphorus	Lactate dehydrogenase (LDH)	
Fasting Lipid panel including fractionated serum cholesterol, triglycerides, total cholesterol, HDL and LDL			
Estimated glomerular filtration (Modification of Diet in Renal Disease) or 24 hr urine creatinine clearance 			
Beta-hCG pregnancy test for appropriate females (serum or urine)			
Coagulation			
Prothrombin time/International normalized ratio (PT/INR)			
Partial prothrombin time (PTT)			
Urinalysis			
Specific gravity			
pH – dipstick			
Glucose – dipstick			
Protein – dipstick			
Blood – dipstick			
Ketones – dipstick			
Microscopic examination required (if blood or protein by dipstick ≥1+)			
Urine total protein to creatinine ratio (UPC ratio) – (if protein by dipstick ≥2+)			

1. Bilirubin fractionation is required if total bilirubin >2x ULN
2. For screening ionized calcium is acceptable
3. The Modification of Diet in Renal Disease Equation will be used to determine an estimated glomerular filtration rate.

Laboratory grades will be reported using the Common Terminology Criteria for Adverse Events (CTCAE v4.0).

For hematology, RBC is not gradable by CTCAE v4.0.

For clinical chemistry, BUN, LDH and estimated creatinine clearance are not gradable by CTCAE v4.0.

For coagulation tests, INR and partial thromboplastin time are gradable by CTCAE v4.0 but prothrombin time is not.

For all laboratory results, displays for hematology, clinical chemistry, and liver function tests will be separately produced.

Summaries of worst case grade increase from baseline grade will be provided for all the lab tests that are gradable by CTCAE v4.0. These summaries will display the number and percentage of subjects with a maximum post-baseline grade increasing from their baseline grade. Any increase in grade from baseline will be summarized along with any increase to a maximum grade of 3 and any increase to a maximum grade of 4. Missing baseline grade will be assumed as grade 0. For laboratory tests that are graded for both

low and high values, summaries will be done separately and labeled by direction, e.g., sodium will be summarized as hyponatremia and hypernatremia.

For lab tests that are not gradable by CTCAE v4.0, summaries of worst case changes from baseline with respect to normal range will be generated. Decreases to low, changes to normal or no changes from baseline, and increases to high will be summarized for the worst case post-baseline. If a subject has a decrease to low and an increase to high during the post-baseline time period, then the subject is counted in both the “Decrease to Low” categories and the “Increase to High” categories.

A supporting listing of all chemistry and haematology laboratory data will be provided.

Unless otherwise specified, the denominator in percentage calculation at each scheduled visit will be based on the number of subjects with non-missing value at each particular visit.

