13.8. Key Elements of Analysis Plan

Data will be listed and summarized according to the GSK reporting standards, where applicable. Data will be listed and summarized mostly by doses. Separate analyses will be provided for Part I and in Part II where applicable. In some instances, analysis may also be generated based on the dose of GSK2879552. Data from Part I and Part II may be combined for some analyses at the end of the trial, for subjects treated at the same dose level. Complete details will be documented in the Reporting and Analysis Plan (RAP). Any deviations from, or additions to, the original analysis plan described in this protocol will be documented in the RAP and final study report.

As it is anticipated that accrual will be spread thinly across centers and summaries of data by center would be unlikely to be information, data from all participating centers will be pooled prior to analysis.

All data up to the time of study completion/withdrawal from study will be included in the analysis, regardless of duration of treatment.

As the duration of treatment for a given subject will depend on efficacy and tolerability, the duration of follow-up will vary between subjects. Consequently there will be no imputation for missing data.

Demographic and baseline characteristics will be summarized.

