13.8.2. Safety Analyses

The All Treated Subjects Population will be used for the analysis of safety data. All serially collected safety endpoints (e.g. laboratory tests, vital signs, electrocardiogram [ECGs]) will be summarized according to the scheduled, nominal visit at which they were collected and across all on-treatment time points using a “worst-case” analysis. Complete details of the safety analyses will be provided in the Reporting and Analysis Plan (RAP).

Safety endpoints are described in Section 2. Complete details of the safety analyses will be provided in the RAP.

A listing by subject including treatment administered, and compliance, will be generated with dates and times of treatment administered. The number of subjects exposed to study drug will be tabulated for Part 1 (for each dose cohort) and Part 2.

All relevant safety data will be listed and summarized according to IDSL standards. The reporting and analysis plan will list the IDSL templates for the displays. Adverse events will be coded and grouped by system organ class (SOC) and preferred (coded) term (PT) using the Medical Dictionary for Regulatory Activities (MedDRA) system for adverse event coding. AEs will be graded according to the National Cancer Institute Common Terminology Criteria for Adverse Events (NCI CTCAE) Version 4.03. Adverse events will be summarized by maximum toxicity grade for each initial dose level. All AEs will be listed. A summary of the number and percent of subjects reporting each AE at least once will be produced for all AEs, for drug-related AEs and for SAEs for Part 1 (for each dose cohort) and Part 2. A listing of those AEs identified as dose-limiting toxicities will also be produced for each dose cohort for Part 1. A listing showing the relationship of AE

verbatim text to group terms and body systems will also be produced. A listing of withdrawals due to AEs will be provided. Deaths and SAEs will be listed should they occur.

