Clinical laboratory evaluations will be performed on the days specified in the Time and Events Table. Clinical chemistry, coagulation, hematology and urinalysis values and change from baseline values will be listed for each subject and flagged high or low relative to their normal ranges, where applicable. The toxicity grade for laboratory data will be calculated using NCI CTCAE Version 4.03. The lab data will then be summarized according to the subject's baseline grade and maximum grade for each cycle of therapy. A listing of subjects with potentially clinically important lab abnormalities will also be produced. A summary of lab values and change from (baseline) may be done for Part 1 (for each dose cohort) and Part 2.

Vital signs and ECG data will be listed and summarized for Part 1 (for each dose cohort) and Part 2. Changes from baseline will be included in the listings and summary.

ECOG Performance Status assessments will be listed and summarized for Part 1 (for each dose cohort) and Part 2.

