### 5.2. Baseline Definitions

- Baseline will be defined as the most recent, non-missing value prior to or on the first study treatment dose date.

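### The SAP swaps the protocol's baseline-grade by maximum-grade laboratory summary for grade increases only, unrecorded and with no stated worst-case denominator, so baseline mix can obscure dose differences in cytopenia

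*SAP*

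**What the plan says.** Protocol Section 13.8.2 grades laboratory data by CTCAE and summarises them by the subject's "baseline grade and maximum grade for each cycle of therapy". The same section says serially collected safety endpoints "will be summarized according to the scheduled, nominal visit at which they were collected and across all on-treatment time points"; the second of these takes the worst case. Protocol Section 13.8 says that departures from the protocol's analysis plan will be documented in the Reporting and Analysis Plan (the SAP) and the study report.

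SAP Section 7.3 describes the gradable laboratory tests differently: "These summaries will display the number and percentage of subjects with a maximum post-baseline grade increasing from their baseline grade". The rows are any increase, then "any increase to a maximum grade of 3 and any increase to a maximum grade of 4". It adds: "Missing baseline grade will be assumed as grade 0". Its only denominator rule, a default that other SAP text could override, is that "the denominator in percentage calculation at each scheduled visit will be based on the number of subjects with non-missing value at each particular visit". The matching hematology display is Table 3.9 (SAP Section 11.10.6), by dose and overall, using a company shell (OLB9C) whose layout is not in the documents.

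SAP Table 1 lists three changes from the protocol: no Part 2 analysis, an abbreviated report, and no ATRA pharmacokinetic analysis. None concerns laboratory data.

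**The concern.** Laboratory change is part of the Part 1 primary endpoint, and Protocol Section 1.4.5.1 names dose-dependent thrombocytopenia as the primary toxicity. Many of these subjects will already have low counts. Protocol Section 1.4.3.2 expects disease-induced pancytopenia, and inclusion criterion 10 sets a WBC ceiling and coagulation limits but no platelet or neutrophil floor.

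A subject at Grade 4 at baseline can never be counted as an increase. One at Grade 3 can never be counted as an increase to Grade 3. A summary by baseline and maximum grade shows these subjects openly, whereas a count of increases alone does not. SAP Section 2.4 says the analysis focuses on comparing dose cohorts. If one cohort enters with more Grade 4 cytopenia than another, the percentages who worsen can differ, or look alike, for that reason alone.

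**Working it through.** **Plan's own figure.** The documents give no rate, denominator or baseline grade distribution for this summary, so there is nothing to reproduce. The question is how the described row behaves.

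**Inputs.**
- N = 7: the number enrolled at 4 mg as of 20 November 2015 (Protocol Section 1.3.5), used only as a realistic cohort size.
- N = 12: the cap for an expanded dose level (Protocol Section 4.2.3).
- f, the share at Grade 4 at baseline: not given; assumed.
- q, the share of subjects below Grade 4 at baseline who reach Grade 4: not given; assumed.

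**Formulas for the Grade 4 row.**
- All subjects in the denominator: (1 − f) × q, with ceiling 1 − f.
- Subjects at risk only: q.
- Share with a Grade 4 maximum, if those at Grade 4 at baseline also have a Grade 4 value afterwards: f + (1 − f) × q.

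**Worked cohort, N = 7.** Suppose 3 start at Grade 4 and 2 of the other 4 reach it.
- All subjects: 2/7 = 28.6%. This row cannot exceed 4/7 = 57.1%.
- At risk: 2/4 = 50.0%.
- Any Grade 4 maximum: (3 + 2)/7 = 71.4%.

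Three different numbers describe the same seven subjects. A baseline-by-maximum table shows all three; the described row shows one, and the SAP does not say which denominator it uses.

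**Two cohorts with the same at-risk rate, q = 0.5, N = 12.**
- None at Grade 4 at baseline: 6/12 = 50%.
- Six at Grade 4 at baseline: 3/12 = 25%.

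The halving comes only from who was enrolled.

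**Sensitivity at q = 0.5.** For f = 0, 0.1, 0.3 and 0.5, the all-subject row is 50%, 45%, 35% and 25%.

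**Missing baseline set to Grade 0.** Each such subject whose true baseline equalled the later maximum adds one false increase: 1/7 = 14.3 points at N = 7. The rule can add increases but cannot remove any.

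For blood counts this should be rare. The Part 1 Time and Events table schedules a CBC at screening and on Day 1 (Day 1 may be skipped only if it was done at a screening visit within 3 days). SAP Section 5.2 says "Baseline will be defined as the most recent, non-missing value prior to or on the first study treatment dose date". Every pre-dose count would have to be absent. The rule has more room to act on chemistry, where screening is the only scheduled pre-dose sample. Magnesium is in SAP Table 2 but not in Protocol Table 5, so the protocol requires no baseline value for it.

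**The case against.** The strongest reply has five parts.

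1. *The denominator is not stated.* A reader might infer that the SAP keeps subjects at Grade 4 at baseline in the percentage. It does not say so: its rule is written for scheduled visits, and the shell is not shown. This stands. What can be said is that no rule excludes them and none defines the worst-case denominator.

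2. *A count of increases is a valid description.* A subject already at Grade 4 did not worsen, and counts appear beside percentages. This stands too. A reader might infer that cytopenia is misreported, but the row can be correct for what it measures and still leave out what the protocol's summary would show.

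3. *The protocol leaves detail to the SAP and asks for worst-case summaries.* True, and its wording does not name a shift table. But reducing the two grades to risen or not risen loses the baseline grade, and no planned table is titled or described as restoring it.

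4. *Other displays cover the gap.* Listing 31 holds every hematology value. Thrombocytopenia, neutropenia and anemia are events of special interest with a summary and listings (SAP Section 7.2), and adverse events are tabulated by maximum grade. This softens the consequence but does not remove it. Protocol Section 8.3 keeps disease-associated abnormalities out of adverse event reporting unless the investigator judges them more severe than expected, so those tables depend on attribution. The listing does not summarise by dose.

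5. *There is no clash with the imputation rule.* A reader might set the Grade 0 convention against the protocol's "Consequently there will be no imputation for missing data". That sentence is drawn from the varying length of follow-up between subjects, so it does not clearly govern a baseline-grade convention. The convention is better described as an addition that Table 1 does not list.

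**Conclusion.** The concern holds in a limited form. The SAP's described laboratory summary departs from Protocol Section 13.8.2, the departure is not logged, and the worst-case denominator is undefined. In a population where Grade 4 counts at entry are plausible, that can obscure differences between small cohorts in worsening cytopenia.

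The size is unknown. The 28.6% against 50% contrast, and the 50% against 25% contrast, rest on assumed values of f and q. The two features also pull in opposite directions: subjects who cannot worsen lower an all-subject percentage, while the missing-baseline rule raises it. No net direction can be claimed.

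A reader might also infer that the dose decision is affected. The documents do not support that. Escalation is driven by dose-limiting toxicities, and the hematologic criterion in Protocol Section 4.2.5 is prolonged myelosuppression with marrow hypoplasia, not a CTCAE grade increase. What is at stake is how clearly an abbreviated, descriptive report shows the main toxicity by dose.

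**What to change.** - For platelets, neutrophils, hemoglobin and WBC, add a table of baseline grade by worst post-baseline grade, by dose, with missing baseline as its own row.
- For the rows counting increases to Grade 3 and to Grade 4, show the at-risk n: subjects below that grade at baseline.
- Record in SAP Table 1 the change from the protocol's summary and the Grade 0 convention, with a reason for each.

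The cost is one extra standard table per test group, from data already collected, and smaller denominators for some percentages.

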### **7.3.1. Liver Function Analyses**

Summaries of hepatobiliary laboratory events including possible Hy’s law cases will be provided in addition to what has been described above.

Possible Hy’s law cases are defined as any elevated (ALT>3×ULN **and** total bilirubin ≥2×ULN (with direct bilirubin ≥35% of total bilirubin, if direct bilirubin is measured)) **OR** (ALT ≥3 times ULN **and** INR >1.5, if INR is measured).

### **7.4. Other Safety Analyses**

The analyses of non-laboratory safety assessment results will be based on GSK Core Data Standards, unless otherwise specified. The details of the planned displays are presented in [Appendix 10: List of Data Displays](#).

Unless otherwise specified, the denominator in percentage calculation at each scheduled visit will be based on the number of subjects with non-missing value at each particular visit.

### **ECG**

A summary of the number and percentage of subjects who had normal and abnormal (clinically significant and not clinically significant) ECG findings will be displayed by scheduled visits as well as for the worst case post-baseline. The summaries for the QTc will use the collected value based on QTcB and QTcF.

The QTcB and QTcF values will be rounded to the integer and the values will be categorized into the following ranges: Grade 0 (<450), Grade 1 (450-480), Grade 2 (481-500), and Grade 3 (≥501). Summaries of grades will display the number and percentage of subjects by grade in the worst case post-baseline. Similarly, grade changes relative to baseline grade will also be generated.

Listings of abnormal ECG findings and a listing of ECG values will be provided.

**Vital Signs**

Changes in heart rate from baseline, Increase in Blood Pressure from baseline and changes in Temperature from baseline will be summarised.

A separate listing of vital signs will also be produced.

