1.3.5. Clinical Safety of GSK2879552

Summary of findings from clinical studies conducted with GSK2879552 can be found in the Investigator Brochure for GSK2879552 [GlaxoSmithKline Document Number [2013N168888_03](#)].

As of 20-NOV-2015, 11 subjects have been enrolled in Part 1 at once daily doses of 1 mg (n=1), 2 mg (n=2), 4 mg (n=7), and 8 mg (n=1). All 11 subjects (100%) had experienced AEs. The most frequently reported AEs (>20%) were fatigue, febrile neutropenia, nausea, anemia, decreased appetite, hypotension, rash, cellulitis, hypokalemia, and local edema. All Grade 4 AEs were hematological and included thrombocytopenia and neutropenia. Treatment-related AEs reported in at least 10% of subjects were nausea, decreased appetite, and thrombocytopenia. The treatment-related thrombocytopenia AEs were Grade 4 in both subjects; one of these subjects also had Grade 3 febrile neutropenia and Grade 3 anemia. Other treatment-related events that were Grade 3 or 4 included anemia and nausea. There were no fatal AEs.

All 11 subjects in Study 200200 have experienced SAEs. The most common SAE was febrile neutropenia. All cases of febrile neutropenia resolved. No other SAEs occurred in more than 1 subject. One subject had fatal pleural effusion secondary to disease under study, which was considered by the investigator to be not related to study treatment.

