4.8.4. Safety Management for ATRA Combination

4.8.4.1. Retinoic Acid syndrome

About 25% of patients with APL treated with ATRA have experienced the retinoic acid-(RA) syndrome characterized by fever, dyspnea, acute respiratory distress, weight gain, radiographic pulmonary infiltrates, pleural and pericardial effusions, edema, and hepatic, renal, and multi-organ failure [ATRA Prescribing Information, 2004]. This syndrome has occasionally been accompanied by impaired myocardial contractility and episodic hypotension. The syndrome generally occurs during the first month of treatment, with some cases reported following the first dose of ATRA.

Retinoic Acid Syndrome should be strongly suspected if the following signs or symptoms (without any other clear or established etiology) emerge during treatment with GSK2879552:

- New or worsening progressive dyspnea or hypoxemia, with increasing demands for supplemental oxygen; respiratory distress refractory to treatment for the initially suspected cause
- Radiologic evidence of new or worsened bilateral pulmonary involvement (infiltrates or opacities) with or without presence of infection, refractory to treatment with anti-infectives (antibiotics, antivirals, antifungals)
- Radiologic evidence of new or worsened pleural or pericardial effusion that is refractory to treatment for an initially suspected cause
- New or worsened peripheral edema, with rapid weight gain (e.g., >5 kg/11 pounds over 7 days)
- Increase in serum creatinine (e.g., >2-fold from baseline)
- The following symptoms or signs may be features of retinoic acid syndrome but if isolated and not accompanied by pulmonary or renal manifestations, may not require rapid initiation of retinoic acid syndrome treatment (unless sufficiently severe and prolonged):
 - Unexplained fever $\geq 38^{\circ}\text{C}$ (100.4°F)
 - Rash of unknown origin
 - Bone pain

- Lymphadenopathy

The measures below are recommended to be taken at the earliest manifestations of suspected retinoic acid syndrome:

- Patients with severe or rapidly progressing retinoic acid syndrome should be hospitalized for continued observation
- In case of uncertainty with the diagnosis, e.g., presence of less specific symptoms of moderate severity, patients should be closely monitored, as the condition may rapidly worsen

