3.15.	All Treated Subjects	SAF_T1	Summary of Maximum QTc Grades Post-Baseline Relative to Baseline		SAC

Safety: Tables					
No.	Population	IDSL / Example Shell	Title	Programming Notes	Deliverable
3.16.	All Treated Subjects	SAF_T1	Summary of Maximum Increase in QTc Grades Post-Baseline Relative to Baseline		SAC
Vital Signs					
3.17.	All Treated Subjects	OVT1B	Summary of Changes in Heart Rate from Baseline		SAC
3.18.	All Treated Subjects	OVT2B	Summary of Increases in Blood Pressure from Baseline		SAC
3.19.	All Treated Subjects	OVT1B	Summary of Changes in Temperature from Baseline	The following categories need to be included: Decrease to <=35 Change to normal or no change Increase to >=38	SAC
ECOG					
3.20.	All Treated Subjects	PS4A	Summary of Change in ECOG 'Performance Status' from Baseline		SAC

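### SAP 7.4 and Table 3.18 summarise blood pressure increases only, so no summary of measured blood pressure can show a fall; protocol 13.8.2 sets no such limit, and SAP Table 1 does not record the departure

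*SAP*

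**What the plan says.** The Vital Signs paragraph of SAP 7.4 reads: "Changes in heart rate from baseline, Increase in Blood Pressure from baseline and changes in Temperature from baseline will be summarised". Heart rate and temperature are described as changes; blood pressure is described as an increase. The display list in SAP 11.10.6 follows suit. Table 3.18 is titled "Summary of Increases in Blood Pressure from Baseline", while Tables 3.17 (heart rate) and 3.19 (temperature) are titled as changes. The programming note for Table 3.19 names both directions: "Decrease to <=35 Change to normal or no change Increase to >=38". Listing 34 gives the vital signs by subject.

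Protocol 13.8.2, on vital signs and ECG data, says: "Changes from baseline will be included in the listings and summary". It also says that serially collected safety endpoints, vital signs among them, are summarised by nominal visit and by a worst-case analysis.

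Protocol 13.8 requires departures from its analysis plan to be documented in the reporting and analysis plan and the final report. SAP 2.1 sends the reader to Table 1 for these. Table 1 has three entries: Part 2 not implemented, an abbreviated report, and no ATRA pharmacokinetic analysis. None concerns vital signs.

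**The concern.** Changes in vital signs are named in the Part 1 primary endpoint (protocol section 2, SAP 2.2). A summary that counts rises only leaves half of the blood pressure data out of the tabulated results, and the reader of the report is not told why.

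The omitted direction is not an idle one. Protocol 1.3.5 includes hypotension in its list of frequent adverse events: "The most frequently reported AEs (>20%) were fatigue, febrile neutropenia, nausea, anemia, decreased appetite, hypotension, rash, cellulitis, hypokalemia, and local edema". Protocol 4.8.4.1 says that retinoic acid syndrome has occasionally come with "impaired myocardial contractility and episodic hypotension", and SAP 5.1 displays one ATRA combination cohort. If readings fell in some subjects without being reported as adverse events, no planned table would show it, and a reader would have to reconstruct the pattern from a listing.

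**Working it through.** The check is mainly a comparison of texts, with one small count. The plan gives no figure of its own to reproduce.

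**Step 1. Is the restriction real or a slip of wording?** It appears twice, in the text of SAP 7.4 and in the title of Table 3.18, each time beside neighbours worded as changes. No other blood pressure table is listed among Tables 3.1 to 3.20.

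- Planned summaries of measured blood pressure: 1 (Table 3.18).
- Of these, able to show a decrease: 0.

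**Step 2. Does the protocol allow it?** Protocol 13.8.2 puts changes from baseline in both the listings and the summary and mentions no direction. A summary of increases covers part of that.

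**Step 3. Is it declared?** None of the three entries in SAP Table 1 covers it. The abbreviated report does not account for it either: the table is still produced, but in one direction.

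**Step 4. Is it consistent with the rest of the SAP?** SAP 7.3 summarises laboratory tests graded at both ends separately by direction, and for ungraded tests counts a subject with both a fall to low and a rise to high in both categories. SAP 11.6.1 applies the same double counting to safety parameters with normal ranges. Temperature has both directions in Table 3.19. Blood pressure is the exception, and no reason is given.

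**Step 5. How many hypotension cases were there?** Inputs from protocol 1.3.5: "As of 20-NOV-2015, 11 subjects have been enrolled in Part 1", and a frequency above 20%. The smallest count k with k/11 > 0.20:

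- 2/11 = 18.2%, which is not above 20%
- 3/11 = 27.3%, which is above 20%

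So k is at least 3. The exact count is not given. If it were 3, the exact 95% confidence interval for 3/11 is 6.0% to 61.0%.

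**Step 6. Where would a fall in blood pressure appear?**

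| Type of fall | AE summaries (Tables 3.1, 3.2) | Table 3.18 | Listing 34 |
|---|---|---|---|
| Reported as an adverse event | Yes | No | Yes |
| Measured, not reported as an adverse event | No | No | Yes |

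The second row is the gap. Protocol 8.3 makes it possible. Clinically significant safety findings are to be recorded as adverse events, but those associated with the underlying disease are not, unless judged more severe than expected. A measured fall put down to the leukaemia could therefore reach neither an adverse event table nor Table 3.18.

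**The case against.** The strongest reply is that hypotension that matters clinically is already tabulated. Protocol 8.3 requires clinically significant vital-sign abnormalities, and any that led to an intervention, to be recorded as adverse events. Those are counted by preferred term in Table 3.2, by maximum grade in Table 3.1 and, where they qualify, in Tables 3.5 or 3.6, all by dose level. This stands, and it rules out a reading that a reader might otherwise take: that hypotension drops out of every summary. It also means that the 3 or more subjects in step 5 are not lost. They are adverse event cases, which the adverse event tables would count.

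A reader might also infer that hypotension is an established risk of GSK2879552. The documents do not support that. The frequency above 20% is all-cause. Hypotension is not among the treatment-related events reported in at least 10% of subjects; since 1/11 = 9.1% and 2/11 = 18.2%, it was judged related in at most one subject. It is absent from the risk table in protocol 1.4.5.1 and from the events of special interest in SAP 7.2. Nor is it the only vital-sign signal: febrile neutropenia is in the same list, and Table 3.19 tabulates fever. The mention under retinoic acid syndrome is of an occasional feature in ATRA-treated patients with promyelocytic leukaemia, and hypotension is not among the signs listed for suspecting the syndrome.

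Third, the cohorts are small (1, 2, 7 and 1 subjects at the November 2015 cut-off), the analysis is descriptive and the study was terminated early. At that size a listing shows much of what a table would. This lowers the stakes, but a listing is still not the summary that the protocol calls for, and adverse event tables depend on the investigator's judgement in a way that measured values do not.

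**Conclusion.** The point holds in a limited form. SAP 7.4 and Table 3.18 narrow the protocol's summary of blood pressure changes to increases, and SAP Table 1 does not say so. No summary of measured blood pressure can show a decrease. The practical loss is confined to measured falls not reported as adverse events; how many there are cannot be told from the documents.

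The count of at least 3 of 11 subjects with hypotension shows that the direction is worth tabulating. It does not measure what would be missed. It assumes that the quoted threshold applies to each event in the list and that all 11 enrolled subjects form the denominator. It would also go too far to say that Table 3.18 would present blood pressure as unremarkable: a table of increases says nothing about decreases.

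**What to change.** Retitle Table 3.18 as Summary of Changes in Blood Pressure from Baseline. Give it decrease as well as increase categories for systolic and diastolic pressure, including worst case post-baseline, by dose level. State the category boundaries in the programming notes, as is done for temperature in Table 3.19, and amend the sentence in SAP 7.4 to match. If the study team prefers to keep increases only, the restriction and its reason belong in SAP Table 1.

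The vital signs are already collected, so the cost is a little programming on one display. Table 3.18 uses shell OVT2B and the heart rate and temperature tables use OVT1B. Neither shell is in the documents, so it cannot be confirmed that OVT2B has a decrease option, and a modified shell may be needed.
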